Attachment 1 RECIST v1.1
Attachment 2: ECOG PS score

# **1** Introduction

## **1.1 Treatment of thyroid cancer**

According to the histological characteristics, thyroid carcinoma can be divided into papillary thyroid carcinoma, follicular carcinoma, medullary thyroid carcinoma (MTC) and anaplastic thyroid carcinoma (ATC). Except that medullary thyroid carcinoma originated from para follicular C cells evolved from nerve spines, the other three originated from thyroid follicular cells. Differentiated thyroid carcinoma (DTC) refers to thyroid papillary carcinoma and thyroid follicular carcinoma, which account for nearly 90% of all thyroid cancers. Patients with DTC have a good long-term survival rate. DTC has a 5-year death rate of about 2% and a recurrence rate of less than 15%; a 10-year mortality rate of 5% and a recurrence rate of 20%; a cumulative 30-year mortality rate of roughly 10% and a cumulative recurrence rate of 30%.

Surgery is the first choice for the treatment of thyroid cancer, especially for DTC, supplemented by thyroid stimulating hormone inhibition therapy and radioactive iodine therapy. There is no effective treatment for unresectable, or metastatic radioiodine resistant thyroid cancer. Most of the patients with DTC have good prognosis and long-term survival after surgery, radioiodine, and thyroid stimulating hormone inhibition therapy. However, there are still a few patients with distant metastasis, and DTC will gradually dedifferentiate in the natural state or during treatment in 1/3 of the patients with distant metastasis, and lose the ability to take iodine, and eventually develop into iodine refractory DTC. The average survival time of patients with iodine refractory DTC is only 3-5 years, and the 10-year survival is about 10%. Thyroid cancer is not sensitive to chemotherapy, only a small number of patients receive chemotherapy. At present, several antiangiogenic drugs for thyroid cancer were under clinical research and achieved good therapeutic efficacy. Sorafenib and lenvatinib were approved by the food and Drug Administration (FDA) on November 22, 2013, and February 13, 2015, respectively. Sorafenib was approved by the China Food and Drug Administration (CFDA) in March 2017 for the treatment of advanced/local

recurrence or metastasis Iodine refractory (RAI) differentiated thyroid cancer (DTC). But until November 2019, lenvatinib still has not been approved for the treatment of thyroid cancer in China.

## **1.2 Apatinib**

Apatinib is a small-molecule VEGFR tyrosine kinase inhibitor, which is invested and developed by Hengrui Pharmaceutical Co., Ltd. with independent intellectual property rights. Its chemical name is N-[4- (1-cyanocyclopentyl) phenyl]-2-[(4-pyridylmethyl) amino-3-pyridylformamide methanesulfonate, with the molecular formula of  $C_{25}H_{27}N_5O_4S$  (molecular weight: 493.58 (methanesulfonate)). Apatinib mainly plays an anti-angiogenic role in the treatment of malignant tumors by inhibiting VEGFR. Preclinical studies have shown that the anti-tumor efficacy of apatinib is better than that of PTK787

The China Food and Drug Administration (CFDA) officially approved the use of apatinib in the treatment of advanced gastric cancer on October 17, 2014.

# **1.3** Research advancement of apatinib in the treatment of thyroid cancer

Ten patients were treated with 750 mg q.d. of apatinib in a single-arm clinical trial for radioiodine refractory differentiated thyroid cancer (RAIR-DTC) initiated by the research team of the Nuclear Medicine Department of Peking Union Medical College Hospital, and nine patients (90 percent) achieved partial response (PR) and one patient achieved stable disease (SD) after eight weeks of treatment. The target lesion's mean diameter was 21.6 mm at baseline and had shrunk by 34% to 12.7 mm after 8 weeks of treatment. The average Tg (Thyroglobulin) level declined by 21% after 2 weeks of treatment; after 8 weeks of treatment, the average Tg level decreased from 1583.5 ng/mL to 294.6 ng/mL, indicating a rapid biochemical reaction. Hand-foot syndrome, hypertension, and hypocalcemia were the most common Grade 3 adverse events (AEs), accounting for 50%, 30%, and 20% of all cases, respectively. 70% of patients had to discontinue apatinib treatment owing to Grade 3 AEs, and 50% had to reduce apatinib dose due to tolerance issues. The study's findings preliminarily confirmed efficacy and safety of apatinib in the treatment of RAIR-DTC.

Therefore, we plan to conduct a multicenter, randomized, double-blind, placebo-controlled clinical study to further prove the efficacy and safety of apatinib in the treatment of locally advanced/metastatic radioiodine refractory differentiated thyroid cancer. The current study will use 500 mg q.d. of apatinib as the initial dose for the safety consideration, based on the previous research results, which suggested possible tolerance concerns with 750 mg q.d. of apatinib in the treatment of patients with RAIR-DTC.

# 2 Study Objectives

# 2.1 Primary Objective

 To assess the efficacy of apatinib compared with placebo, as measured by progression-free survival (PFS) according to Response Evaluation Criteria in Solid Tumors (RECIST) Version 1.1 criteria.

# 2.2 Secondary Objectives

- To assess the overall survival (OS) in subjects treated with apatinib, compared with placebo.
- To assess the objective response rate (ORR) in subjects treated with apatinib, compared with placebo.
- To assess the disease control rate (DCR) in subjects treated with apatinib, compared with placebo.
- To assess the duration of response (DOR) in subjects treated with apatinib, compared with placebo.
- To assess the time to response (TTR) in subjects treated with apatinib, compared with placebo.
- To assess the safety and tolerability of apatinib, compared with placebo.

# 3 Study Design and Methodology

# 3.1 Overall Study design

This is a multicenter, randomized, double-blind, placebo-controlled clinical trial to evaluate the efficacy and safety of apatinib in the treatment of locally advanced/metastatic radioiodine refractory differentiated thyroid cancer (RAIR-DTC).

The eligible subjects will be randomly assigned to either the treatment group or control group in a 1:1 ratio. Apatinib or placebo will be given 500 mg orally once daily for 28 days. Apatinib treatment will be discontinued at the time of disease progression, intolerable toxicity, withdrawal of consent, or due to investigator's evaluation. Tumor imaging with CT or magnetic resonance imaging (MRI) will be done at the end of first and second treatment cycles, then every two treatment cycles thereafter. The efficacy will be assessed per RECIST version 1.1 by investigators. Safety assessment including vital signs, physical examination, blood and urine analysis, liver, kidney and thyroid function tests, electrolyte profile, electrocardiogram and ECOG performance status will be done every two weeks for one-two cycles, and at the end of each subsequent cycle. Adverse events will be graded according to the National Cancer Institute Common Terminology Criteria for Adverse Events (version 4.0). Survival status will be followed up every two months until death or loss to follow-up.

In the extension phase, subjects in the Apatinib group will continue the treatment when anticipated to benefit from apatinib treatment. For the subjects in the control group, they will be allowed to receive apatinib upon experiencing radiographic disease progression (PD) per RECSIT v1.1 by investigator. Extended treatments are terminated after progression disease, intolerable toxicity, and withdrawal of informed consents during extension phase.

## 3.3 Sample Size

Sample size determination is performed by PASS 11 software with group sequential log-rank test settings. Assuming a median PFS of 5.8 months in control group, and a median PFS of 12 months in treatment group; subjects randomly assigned to two group by a ratio of 1:1, with an enrollment time of 24 months and a follow-up of 12 months; 50 subjects in each group, to observe 37 PFS events in the treatment group and 46 PFS events in the control group, will provide 90% power to detect a difference between groups using a log-rank test with a two-sided significance level ( $\alpha$ )=0.05. With a 15% drop-out rate, each group will require 59 people, for a total sample size of 118 subjects.

# **4 Study Population**

### 4.1 Study Population

This is a multicenter, randomized, double-blind, placebo-controlled clinical trial to observe and evaluate the efficacy and safety of apatinib in the treatment of locally advanced/metastatic radioiodine refractory differentiated thyroid cancer (RAIR-DTC).

# 4.2 Inclusion Criteria

1. Age:  $\geq$  18 years old, both male and female.

2. Locally advanced or metastatic differentiated thyroid carcinoma (papillary, follicular, Hurthle cells, poorly differentiated carcinoma) with at least one measurable lesion after treatment (according to RECIST Version 1.1 standard, the measurable lesion with a long diameter≥10 mm or an enlarged lymph node with a short diameter≥15 mm; According to RECIST Version 1.1 standard. Previously treated lesions can be used as the targeted lesion after the progression is confirmed.

- 3. Progressive disease has occurred within 12 months before enrollment (by RECIST Version 1.1).
- 4. Radioiodine refractory (meet one of the following requirements)
  - a) The targeted lesion completely has lost the capacity of iodine uptake during radioiodine therapy
  - b) The subjects have received a single dose of radioiodine ( $\geq 3.7 \text{ GBq} \geq 100 \text{mCi}$ ) within 12 months and the progressive disease has occurred.

c) The interval between two radioiodine therapies is less than 12 months, and the dose is more than  $3.7 \text{ GBq} \ge 100 \text{ mCi}$ , and the progressive disease has occurred over 12 months after iodine treatment at least one time

- d) Cumulative dose of radioiodine  $\geq 22.2 \text{ GBq} (\geq 600 \text{ mCi}).$
- 5. The function of the main organs is normal and meets the following requirements:

Blood routine: (no blood transfusion within 14 days)

- a) Hb≥90g/L;
- b) ANC  $\geq 1.5 \times 10^{9}/L$ ;
- c) PLT  $\geq 80 \times 10^{9}/L$ ;

Biochemical examination should meet the following standards

a) BIL < 1.5 folds limit of normal (ULN)

b) ALT and AST  $< 2.5 \times$  ULN, ALT and AST  $< 5 \times$  ULN if liver metastasis.

c) Serum Cr  $\leq$  1 × ULN, endogenous creatinine clearance rate  $\geq$  50ml / min (Cockcroft Gault formula)

6. ECOG PS: 0-2 points.

7. The estimated survival  $\geq$  3 months.

8. Women of childbearing age must have pregnancy test (serum) (-) within 7 days before enrollment. In addition, appropriate contraceptive methods should be used voluntarily during the observation period and within 8 weeks after the last administration of apatinib tablets; for men, it should be surgical sterilization, or agree to use appropriate contraceptive methods during the observation period and within 8 weeks after the last administration of apatinib tablets.

9. Subjects volunteered to join the study and signed the informed consent form (ICF).

10. Subjects with good compliance, who can be followed up and report AEs according to the requirements of the protocol.

## 4.3 Exclusion Criteria

1. Histological subtypes of thyroid carcinoma other than differentiated type (such as medullary carcinoma, lymphoma, or sarcoma).

2. Subjects who have used VEGFR-TKI, such as vandetanib, cabozantinib, lenvatinib, sunitinib, sorafenib, etc. within 1 month before the first dose of study treatment.

3. Heart diseases that cannot be well controlled, such as: (1) cardiac insufficiency (grade 2 or above) according to the New York Heart Association (NYHA) standard, or cardiac color Doppler ultrasound examination: LVEF (left ventricular ejection fraction) < 50%; (2) unstable angina pectoris; (3) myocardial infarction within 1 year before the beginning of the study; (4) clinically significant supraventricular or ventricular arrhythmia, which need treatment or intervention: (5) QTc > 450ms (male); QTc > 470ms (female) (QTc interval is calculated by Fridericia formula); the average of three measurements is calculated with an interval of 2 minutes if QTc is abnormal; (6) subjects with hypertension who cannot be reduced to the normal range after anti-hypertension drug

treatment (SBP  $\geq$  140mmHg or DBP  $\geq$  90mmHg) (based on the average value of BP readings obtained from  $\geq$  2 measurements), the above parameters can be achieved through anti-hypertension treatment.

4. Factors affecting oral drug absorption (such as inability to swallow, nausea and vomiting, chronic diarrhea, and intestinal obstruction, etc.).

5. Subjects with the risk of gastrointestinal bleeding should not be included in the study, including:
(1) subjects with active peptic ulcer lesions and occult blood in stool (+ +); (2) subjects with a history of melena and hematemesis within 3 months.

6. Abnormal coagulation function (INR > 1.5, APTT >  $1.5 \times ULN$ ) with bleeding tendency.

7. Obvious hemoptysis within 2 months before screening, or the amount of hemoptysis reached half a teaspoon (2.5ml) or more every day.

8. Arteriovenous thrombosis events occurred within 12 months before screening, such as cerebrovascular accident (including transient ischemic attack, cerebral hemorrhage, cerebral infarction), deep vein thrombosis and pulmonary embolism, etc.

9. Received radiotherapy for thyroid carcinomas within 28 days before screening.

10. Subjects with active bleeding, ulcer, intestinal perforation, intestinal obstruction, and surgery within 28 days before screening (the wound must have recovered completely if the operation is performed before 28 days or more).

11. Uncontrollable infections during screening.

- 12. Pregnant or lactating women.
- 13. Subjects with depression (HAMD score  $\geq$  17, see Appendix 5).

14. Subjects who are not suitable for the study.

# 4.4 Shedding/rejection criteria

1. The effectiveness and / or safety evaluation cannot be carried out due to the failure of medication

according to the provisions of this protocol.

- 2. Using other anti-tumor drugs during the study.
- 3. Do not meet the Inclusion/exclusion criteria.

# 4.5 Termination Criteria

Termination of the treatment does not mean the withdrawal from the study. Subjects must continue to complete the remaining study visits as required by the protocol. If the subject meets any of the following criteria, the treatment must be terminated:

- 1. Subjects withdraw their informed permission and request to be removed from the study.
- 2. Progressive disease is confirmed by investigator.
- 3. Pregnancy during the study.
- 4. the subjects cannot tolerate the toxicity after dose adjustment.
- 5. Other situations indicating the need to withdraw from the study.

# **5** Study Treatment

# 5.1 Treatment and Administration

#### 5.1.1 Study Drug introduction

The study drug is provided by Jiangsu Hengrui Pharmaceutical Co., Ltd and the specific information is shown in the table below.

#### Information of the drug

Drug	apatinib mesylate tablet	apatinib mesylate tablet simulator (placebo)
Dosage form	tablet	tablet
Specification:	250 mg	-

Storage	sealed and protected from light, stored under 25°C	sealed, protected from light, stored below 25°C
Administration route	oral	oral
Manufacturer	Jiangsu Hengrui Pharmaceutical Co., Ltd.	Jiangsu Hengrui Pharmaceutical Co., Ltd.

#### 5.1.2 Administration regimen

- Group A (apatinib group): apatinib mesylate 500mg (250mg/tablet, 2 tablets), po, q.d.; after meals (try to take at the same time every day), 4 weeks as a cycle.
- Group B (control group): 2 tablets of apatinib mesylate mimic, po, q.d.; after meals (try to take at the same time every day), 4 weeks as a cycle.

Until the patient's progressive disease, the toxicity becomes unacceptable, the patient withdraws informed consent, or the researcher determines that the medicine must be stopped, the drug should be halted.

#### 5.1.3 Preservation, distribution, and management of the study drug

Special staff should oversee the drug's management, distribution, and recovery in this research trial. The study drugs should be kept sealed, away from light, and at a temperature below 25°C. There is a 24-month validity term. The researcher must guarantee that the study drugs are only administered to the clinical trial participants, and that the dosage and administration follow the protocol. The leftover study drugs should be returned to Jiangsu Hengrui Pharmaceutical Co., Ltd., and no non-clinical study participants should be given the drug.

At the moment of drug distribution, two people should sign the drug receipt form. One copy each should be kept by the clinical research unit and Jiangsu Hengrui Pharmaceutical Co., Ltd. The remaining study drugs and empty boxes should be collected at the end of the study, and both parties should sign the drug recycling form. Each drug's distribution and recovery should be recorded on a separate record sheet in real time.

The inspector is in charge of ensuring that the leftover study drugs in clinical trials are supplied,

used, stored, and disposed of properly.

#### 5.1.4 Study drug destruction

The total quantity of the drug is 120% of the designed dosage, and the remaining drug should be recovered by the inspector and returned to Jiangsu Hengrui Pharmaceutical Co., Ltd.

The researcher can trash the used study drugs and empty boxes without harming the public's health after alerting the sponsor in writing. All drug handling should be documented by the investigator.

These records must show the certificate and quantity of each batch of destroyed drug, as well as the method of disposal (in accordance with the requirements of local laws), as well as the personnel handling the drug.

# 5.2 Study Drug Dose Modification

#### 5.2.1 Dose

The initial dose of the drug is 500mg, oral, once a day.

If AEs of Grade 3 or higher occur during treatment, the dose should be discontinued or reduced. As a cycle, the minimum dose can be reduced to 250mg once a day for 28 days.

When the dose is modified in each administration cycle, the dose is suspended first to guarantee consistency over the whole research. If the individuals still cannot tolerate the dose after taking the dose suspension measurement, the dose is reduced.

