#### 5.2.2 Dosage adjustment

The criteria of dose suspension or reduction are as follows:

- Dose suspension and dose reduction can be carried out, only when the hematologic toxicity and non-hematological toxicity reach Grade 3 (special AEs such as hypertension, drug suspension or adjustment should be specified separately)
- > in non-hematological toxicity, subjects received active symptomatic treatment for subjects with

weight loss, nausea, vomiting, alopecia, fever with definite causes (such as infection), and elevated alkaline phosphatase (AKP) (Grade 3/4) without dose suspension and/or dose reduction.

➤ for hypertension AEs, antihypertensive drugs should be started and/or added when blood pressure is confirmed to be elevated (systolic blood pressure ≥ 140 mmHg or diastolic blood pressure ≥ 90 mmHg). If the blood pressure remains good (systolic blood pressure < 140 mmHg or diastolic blood pressure < 90 mmHg), the drug use can be continued. If systolic blood pressure ≥ 160 mmHg or diastolic blood pressure ≥ 100 mmHg still exists after the maximum dose of antihypertensive drug treatment, the drug administration should be interrupted; if the systolic blood pressure ≤ 150 mmHg and diastolic blood pressure ≤ 95 mmHg, and the subject has received the stable dose of antihypertensive drugs for at least 48 hours, the dosage can be reduced to 250mg.

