#### 5.2.4 Dose reduction

Dose adjustment is made at any time in each administration cycle. After the dose is reduced, it should not be brought back to the previous level. After the dose is adjusted to 250 mg q.d., continued dose adjustment is not allowed, including dose increase or decrease for any reason, but dose suspension is still allowed.

AE classification	NCI	Dose adjustment
		stop medication and continue to use the original dose when
Hematology AE	Grade 3	the AE $\leq$ Grade 2. If Grade 3 or above AEs occur again, the
		drug should be continued after a-dose reduction

Table 1 principle of dose adjustment of apatinib
--

	Grade 4	the drug is suspended, and the drug is continued after a-dose
		reduction and the AE recovered to $\leq$ Grade 2.
Non-hematological AE	Grade 3	The drug should be suspended until the AE $\leq$ Grade 1, and the
		drug should be continued with the original dose; if Grade 3 or
		above AEs occurs again, the drug should be continued after a-
		dose reduction.
	Grade 4	the drug is suspended, and the drug is continued after a-dose
		reduction and the AE recovered to $\leq$ Grade 1.

Note: the above evaluation is carried out according to NCI-CTCAE4.0

For subjects with gastrointestinal perforation, wound dehiscence, fistula, severe bleeding, nephrotic syndrome or hypertensive crisis, administration should be stopped permanently. Subjects with moderate to severe proteinuria or severe hypertension who need further diagnosis should stop using the drug temporarily.

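### Sections 5.2.1 and 5.2.4 (Table 1) give different restart doses after a first Grade 4 adverse event, and neither refers to the list of exempted events in 5.2.2

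*Protocol*

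**What the plan says.** All passages are in the protocol.

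- **Section 5.2.1.** On the starting dose: "The initial dose of the drug is 500mg, oral, once a day". On the only lower level: "As a cycle, the minimum dose can be reduced to 250mg once a day for 28 days". On the trigger: "If AEs of Grade 3 or higher occur during treatment, the dose should be discontinued or reduced". On the order of steps, which is given a study-wide purpose: "the dose is suspended first to guarantee consistency over the whole research". On when to reduce: "If the individuals still cannot tolerate the dose after taking the dose suspension measurement, the dose is reduced". The section does not separate Grade 3 from Grade 4 and names no exempt event.
- **Section 5.2.2.** The general criterion is "Dose suspension and dose reduction can be carried out, only when the hematologic toxicity and non-hematological toxicity reach Grade 3", with special events such as hypertension to be handled separately. A following bullet lists weight loss, nausea, vomiting, alopecia, fever with a definite cause and "elevated alkaline phosphatase (AKP) (Grade 3/4) without dose suspension and/or dose reduction"; these receive symptomatic treatment only.
- **Section 5.2.4, Table 1.** For a Grade 3 event the drug is stopped, restarted at the original dose, and reduced if an event of Grade 3 or above comes back. For a Grade 4 event, in both the hematology and the non-hematological rows, "the drug is suspended, and the drug is continued after a-dose" reduction once the event has recovered to the stated grade. The note to the table cites only the CTCAE version.
- **Section 5.2.4, text.** A reduced dose is not raised again. At 250 mg only suspension remains possible.

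**The concern.** A dose-modification rule has to give each site the same instruction for the same event. In 5.2.1 reduction depends on the subject failing to tolerate the dose after a suspension. In the Grade 4 rows of Table 1 it is unconditional at the first event. Neither section refers to the other, and no order of precedence is stated.

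Two things are at stake. The first is subject management: after a first Grade 4 toxicity the section followed decides the restart dose, and a reduction then holds for the rest of treatment. The second is interpretation: Section 10.2.2 plans a summary by group of adverse events leading to dose adjustment. If sites follow different sections, that summary and the dose received in the apatinib arm would partly reflect which section was read.

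**Working it through.** There is no stated figure to reproduce; the check is a comparison of the sections by type of event, for a subject still on 500 mg.

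**1. First Grade 4 event with no rule of its own.** This leaves out hypertension (5.2.2), proteinuria (6.2.4), the events that stop drug permanently (text below Table 1) and the list in 5.2.2.
- 5.2.1: suspend. It names no restart dose, but because reduction is reserved for subjects who still cannot tolerate the dose, restart is at the dose already held, 500 mg.
- 5.2.2: allows suspension and reduction from Grade 3, sets no order and has no separate Grade 4 rule. It does not settle the matter.
- Table 1: suspend, then restart at the reduced dose. The only reduced level is 250 mg.
- Result: two restart doses, with a ratio of 500 / 250 = 2.

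**2. Grade 3 event not on the 5.2.2 list.**
- 5.2.1: suspend, then reduce if the dose is still not tolerated.
- Table 1: suspend, restart at the original dose, reduce on recurrence.
- Result: the two sequences agree, since recurrence after restart is a failure to tolerate the dose after suspension.

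**3. Grade 3 or 4 event on the 5.2.2 list.**
- 5.2.2: no suspension and no reduction.
- 5.2.1: the sentence on Grade 3 or higher applies without exception.
- Table 1, non-hematological rows: suspend at Grade 3; suspend and reduce at Grade 4. No exemption is noted.
- Result: the sections agree only if 5.2.2 is read as an exception to the other two. Taken literally they differ.

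**4. Number of subjects.** This would require the rate of first Grade 4 events at 500 mg, and the rate of Grade 3/4 events on the list. The protocol gives neither. Section 1.3 reports dose reduction in 50% of ten patients, but at 750 mg, for tolerance in general and not by grade. The most common Grade 3 events it names (hand-foot syndrome, hypertension, hypocalcemia) are not on the 5.2.2 list. No estimate is made.

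**The case against.** The strongest reply is that Table 1 is the detailed version of a general statement. Its Grade 4 rows also suspend first, so the order in 5.2.1 is kept, and the opening sentence of 5.2.1 allows reduction from Grade 3 upward. This narrows the conflict without removing it. The last sentence of 5.2.1 still makes reduction conditional where Table 1 makes it automatic. 5.2.1 is framed as the rule for the whole study, and nothing says that the table overrides it.

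For the listed events the reply is stronger. 5.2.2 sets out when modification applies, Table 1 sets out how, and a specific list is naturally read as an exception. That largely stands. What remains is that two sections contradict the list literally and neither points to it, so a site working from Table 1 alone would miss it.

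Three stronger readings are tempting but not supported:

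- A reader might infer that any Grade 4 event has three possible outcomes, including continued full dosing. No section orders dosing through an ordinary Grade 4 event. That outcome arises only for the listed events, and three outcomes appear only for Grade 4 events on the list when each section is read in isolation.
- A reader might infer that 5.2.1 restarts the suspend-first sequence in every cycle, and so conflicts with Table 1 on a Grade 3 event that recurs in a later cycle. The reference to each administration cycle need not mean a reset; 5.2.4 uses the same phrase to mean in any cycle.
- A reader might infer damage to the primary test. Sections 10.1 and 10.2.1 analyze PFS in the full analysis set whatever dose was received, and nothing in the protocol shows an effect on that comparison.

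**Conclusion.** The contradiction is real and limited. For a first Grade 4 event with no rule of its own, 5.2.1 leads to restart at 500 mg and Table 1 to restart at 250 mg, with no stated precedence and no way back after a reduction. The missing link between the 5.2.2 list and the other two sections is a smaller defect of the same kind.

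The difference is two-fold in daily dose for each subject concerned. How many subjects that would be is unknown. The conclusion rests on reading the condition in 5.2.1 as written, namely that without continued intolerance there is no reduction. That sites would in fact diverge is a risk created by the wording; the protocol offers no evidence that they did. No view is taken on which instruction is clinically right.

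**What to change.** Reconcile Section 5.2.1, Section 5.2.2 and Table 1 of Section 5.2.4 in one amendment so that:

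- they give one consistent instruction for a first Grade 4 event;
- they give one consistent instruction for the events listed in 5.2.2; and
- each section refers to the others, including the separate rules for hypertension, proteinuria and permanent stopping.

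The sponsor's medical lead decides the clinical content. The cost is amendment wording and brief site retraining.
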